## **3. Description of study population**

The study population will be described overall and in each hospital separately.

### **3.1. Patient accounting**

Details of patients screened, those who meet the study inclusion criteria, those who are eligible and randomized, those who are eligible but not randomized, those who withdraw from the study after randomization and those who are lost to follow-up will be summarized in a CONSORT flow diagram. The number (%) of patients attending scheduled follow-up visits by study day will be reported.

### **3.2. Description of study population**

Patients in each treatment group, overall and by hospital, will be described with respect to baseline characteristics. The description will be in terms of medians and interquartile ranges for continuous characteristics and using counts and percentages for categorical characteristics. The clinical importance of any imbalance will be noted but statistical tests of significance of baseline imbalance will not be undertaken.

## **4. Description of patient populations and outcomes**

### **4.1. Patient populations**

We will analyse the efficacy data using Intention-to-Treat and Per-Protocol approaches, with Intention-to-Treat as primary approach. Safety analysis will be performed using an all-patients-treated approach, including all patients who received

at least a single dose, and according to the treatment regimen actually received. Patients who receive a second treatment regimen will be included in the Intention-to-Treat analysis with their outcome after the first treatment regimen, but excluded from the Per-Protocol analysis.

#### *4.1.1. Intention to treat (ITT) analysis*

In the Intention-to-Treat analysis, all patients will be analysed according to their randomized allocation, even in case they receive another treatment regimen, show protocol violations prior to or during the study. Patients lost-to-follow-up before the 12 month post treatment follow-up or who do not provide a sputum are considered to be adverse treatment outcomes in this analysis, unless they are known to have moved out of the study region.

#### *4.1.2. Per protocol (PP) analysis*

In the per-protocol analysis only patients who receive study drug as planned, receive a treatment regimen only once, have complete follow-up (till 2.5 years or development of a study endpoint) or have reached a study endpoint at an earlier time-point, and follow the protocol as planned are included.

In Table 2 the protocol violations are classified as minor and major where minor violations can be included in the PP analysis population and major violations are excluded.

**Table 2:** The protocol violations classified as minor or major violation

Protocol Violation	Major/Minor Violation	Comments
Inclusion criteria		
1. Smear-positive pulmonary TB	Major	
2. 15 years or older	Major	
3. Able and willing to provide written informed consent	Major	
Exclusion criteria		
1. MDR-TB diagnosed with resistance on rapid DST for rifampicin prior to start of treatment	Major	
2. Extra-pulmonary TB, smear-negative TB	Major	
3. Patients in need of hospitalization because of very bad general condition or complications at screening	Major	
4. Patients with clinically active liver disease at screening	Major	
5. Known HIV-positives	Major	
6. Known hepatitis B or C infected patients	Major	
7. Pregnant women	Major	
Treatment violations		
1. Missing at least a full day of treatment	Minor	
2. Not following the randomized regimen	Major	
Follow-up violations		
1. Missing study endpoint	Major	

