We expect that the standard pulmonary TB treatment regimens recommended by the Union² can be optimized by using daily high dose rifampicin during Cat. 1 primo-treatment. For the here proposed pilot study, dosing of rifampicin would be doubled, while standard dose isoniazid, pyrazinamide and ethambutol would be maintained. Management decisions would be made after 2 weeks of intensive phase, based on remaining numbers and decline of TB bacilli on microscopy for AFB [auramine and fluorescein diacetate (FDA) vital staining]. Those with min. 1 log decline in the number of AFB by FDA smear, or already negative, would continue the unaltered regimen. Those not meeting these criteria would be referred for rapid DST by slide DST and/or Xpert MTB/RIF, depending on ease of referral. In case no rifampicin resistance is detected they would continue the optimized Cat. 1 treatment, with further monitoring by smear and rapid DST as per National TB Programme (NTP) indications, i.e. rapid DST in case a smear is positive at 3, 5 or 6 months; those diagnosed with rifampicin resistance at any time and by any technique would be switched immediately to the standard short "Bangladesh" MDR-TB treatment regimen. In the control arm, referral for rapid DST would be based on non-remittance of fever at the end of the second week, otherwise treatment management remains the same. Failures, relapses and other recurrences of the first-line regimen would all undergo rapid DST, and if not found to be rifampicin resistant they would be re-started on the same 6-month Cat. 1. The current Cat. 2 first-line retreatment regimen would no longer be used in the intervention arm.

Intervention and control treatment regimens (Rh: double dose rifampicin)

New cases	
- intervention:	2 HRhZE / 4 HRh
- control:	2 HRZE / 4 HR (Cat. 1 regimen)
Retreatment cases	
- intervention:	2 HRhZE / 4 HRh
- control:	2 SHRZE / 1HRZE / 5 HRE (Cat. 2 regimen)
MDR patients detected at any time	
	4 KHPtoGCEZ / 5 GCEZ (MDR regimen)

The expected benefits from this optimized treatment regimen cascade are:

1. Reduced occurrence of relapse with susceptible bacilli in patients with extensive disease, due to better sterilizing activity while maintaining the same treatment duration. Total absence of relapse with AFB smear at 2 weeks negative or scanty would suggest that shortening of the regimen to 4 months could be tried for fast converters.

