 - refer for rapid DST if indicated by algorithm; switch to MDR if rifampicin resistant
 - otherwise continue high-dose treatment
 - o **Control arm only:**

- refer for rapid DST if still fever (temperature $\geq 38^{\circ}\text{C}$); switch to MDR if rifampicin resistant
 - Enquire, register adverse effects. Stop all drugs and refer in case of hepatitis suspicion (feeling sick, anorexia, vomiting, jaundice)
- Visit after four weeks V3: intervention + control arm
 - Clinical check, weight, temperature: improved signs and symptoms of TB?
 - Give treatment, record attendance
 - Liver test
 - Enquire, register adverse effects. Stop all drugs and refer in case of hepatitis suspicion (feeling sick, anorexia, vomiting, jaundice)
- Visit after 2 months V4: intervention + control arm
 - Clinical check, weight, temperature: signs and symptoms of TB absent?
 - Give treatment, record attendance
 - Cat. 1: sputum smear for AFB
 - Refer for rapid DST if AFB-positive (auramine and FDA) and clinically poor evolution; switch to MDR treatment if rifampicin resistant
 - Liver test
 - Enquire, register adverse effects. Stop all drugs and refer in case of hepatitis suspicion (feeling sick, anorexia, vomiting, jaundice)
- Visit after 3 months V5: intervention + control arm
 - Clinical check, weight, temperature: signs and symptoms of TB absent?
 - Give treatment, record attendance
 - Sputum smear for AFB: all Cat. 2 and Cat. 1 patients positive at month 2
 - Refer for rapid DST if AFB-positive (auramine and FDA); switch to MDR treatment if rifampicin resistant
 - Enquire, register adverse effects. Stop all drugs and refer in case of hepatitis suspicion (feeling sick, anorexia, vomiting, jaundice)
- Visit after 4 months V6: intervention + control arm
 - Clinical check, weight, temperature: signs and symptoms of TB absent?
 - Give treatment, record attendance
 - Sputum smear for AFB: Cat. 2 positive at month 3 only
 - Refer for rapid DST if AFB-positive; switch to MDR treatment if rifampicin resistant
 - Enquire, register adverse effects. Stop all drugs and refer in case of hepatitis suspicion (feeling sick, anorexia, vomiting, jaundice)
- Visit after 5 months V7: intervention + control arm
 - Clinical check, weight, temperature: signs and symptoms of TB absent?
 - Give treatment, record attendance
 - Sputum smear for AFB: all patients
 - Declare failure if positive and refer for rapid DST if AFB-positive
 - Switch to MDR treatment if rifampicin resistant

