 - Rifampicin sensitive:
 - Control arm: start Cat. 2
 - Intervention: re-start Cat. 1
 - Enquire, register adverse effects. Stop all drugs and refer in case of hepatitis suspicion (feeling sick, anorexia, vomiting, jaundice)
- Visit after 6 months (or 8 months for Cat. 2) V8: intervention + control arm
 - Clinical check, weight, temperature: signs and symptoms of TB absent?
 - Stop treatment, record attendance
 - Sputum smear for AFB: all patients
 - Declare cured if negative and inform about signs of relapse
 - Declare failure if positive and refer for rapid DST if AFB-positive

- Switch to MDR treatment if rifampicin resistant
- Rifampicin sensitive:
 - Control arm: re-register, start Cat. 2
 - Intervention: re-register, re-start Cat. 1
- Enquire, register adverse effects
- Make appointment for check-up after 12 months

- Visit 12 months after end of treatment V9 (intervention + control arm cured or defaulted)

- Reminders, home visit if not attending
- History from relatives / neighbours if not met (retreated or died of TB?)
- Clinical check: signs and symptoms of TB absent?
- If attending at the clinic only: weight, temperature
- Sputum smear and culture for AFB
 - If negative: further passive follow-up
 - If positive: declare relapse and refer for rapid DST
 - Switch to MDR treatment if rifampicin resistant
 - Rifampicin sensitive:
 - Control arm: re-register, start Cat. 2
 - Intervention: re-register, re-start Cat. 1

All enrolled patients will be monitored intensively for drug toxicity (clinical; liver enzymes during the first 2 months). Treatment will be interrupted in case of a serious adverse event, possibly due to the TB drugs, and patients referred to the nearest project hospital. In case of toxic hepatitis, after full recovery drugs will be re-introduced in hospital one by one, aiming at re-starting the same regimen since this toxicity is often transient and probably not rifampicin dose-related.

Unscheduled visits can take place at any time during the patients participation in the study. During these visits, all study procedures will be performed if needed, and data will be collected.

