8.3 Statistical methods

8.3.1 Analysis populations

We will analyse the efficacy data both using Intention-to-Treat and Per-Protocol approaches, with Intention-to-Treat as primary approach. In the Intention-to-Treat analysis, all patients will be analysed according to their randomized allocation, even in case they receive another treatment regimen, show protocol violations prior to or during the study, or are lost-to follow. Patients lost-to-follow-up before the 12 month post treatment follow-up or who do not provide a sputum smear are considered to be failures in this analysis, unless they are known to have moved out of the study region. In the per-protocol analysis only patients who receive study drug as planned, have complete follow-up (till 2.5 years or development of a study endpoint) or have reached a study endpoint at an earlier time-point, and follow the protocol as planned are included.

Safety analysis will be performed using an all-patients-treated approach, including all patients who received at least a single dose, and according to the treatment regimen actually received.

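### The SAP's single-regimen condition for the per-protocol set has no time limit, so failures and relapses treated as planned are removed because they reached the endpoint

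*SAP*

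**What the plan says.** SAP 4.1.2 defines the PP set by several conditions that must all be met. Among them, patients must "receive a treatment regimen only once, have complete follow-up (till 2.5 years or development of a study endpoint) or have reached a study endpoint" before then. SAP 4.1 states the same rule for both populations: a patient who receives a second regimen stays in ITT with "their outcome after the first treatment regimen, but excluded from the Per-Protocol analysis". Neither sentence says when the second regimen must start for the exclusion to apply.

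Protocol 8.3.1 has no single-regimen condition. It admits "only patients who receive study drug as planned, have complete follow-up (till 2.5 years or development of a study endpoint") or an earlier endpoint, provided the protocol was followed.

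Protocol 5.3 makes a further regimen part of planned care after a bacteriological endpoint. At months 5 and 6 (or 8) the instruction is "Declare failure if positive and refer for rapid DST if AFB-positive". At the visit 12 months after treatment it is "If positive: declare relapse and refer for rapid DST". Rifampicin-resistant patients then go to the MDR regimen. For sensitive patients the end-of-treatment and 12-month visits specify "Control arm: re-register, start Cat. 2" and "Intervention: re-register, re-start Cat. 1", and month 5 has the equivalent. Protocol 1.1 likewise foresees re-treatment of failures and relapses: "if not found to be rifampicin resistant they would be re-started on the same 6-month Cat. 1".

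Failure and relapse are both components of the primary endpoint (SAP 4.2), and SAP 6 reports results by outcome category as well as for the composite.

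**The concern.** Membership of an analysis set should not depend on the outcome being analysed. Here a patient who fails or relapses, and is then managed exactly as the protocol directs, receives a second course and so meets the exclusion. The words admitting patients who have already reached an endpoint do not help, because they relax only the follow-up condition. The single-regimen condition still applies.

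The rule acts selectively. It takes out failures and relapses, the outcomes the higher rifampicin dose is chiefly meant to reduce, and leaves deaths in. The PP table by category would show few or no failures and relapses in either arm. A reader could take that as what happens when patients adhere, when it is produced by the population definition.

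**Working it through.** **1. The text.** The conditions in SAP 4.1.2 are cumulative. The SAP already deals elsewhere with most regimen changes before an endpoint:
- Switches to the MDR regimen before any outcome are excluded from the outcome analysis (4.2).
- A change of at least two drugs for adverse events is itself a failure (4.2).
- Not following the randomized regimen is a major violation (Table 2).

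What the single-regimen clause mainly adds is therefore the removal of patients re-treated after an endpoint. The wording of 4.1 supports this, since it speaks of patients who already have a first-regimen outcome.

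**2. Inputs (Protocol 8.4).** Control rates are failure 2%, relapse 2%, default 4% and death 4%, with 500 patients per arm. The components sum to 12%, although the planned contrast is stated as 10% against 7%, so shares are given on both bases. The plan's 1,421 per arm for that contrast is reproduced by the two-proportion formula with continuity correction (two-sided 5%, 80% power; 1,422 after rounding up). That figure does not depend on the PP rule.

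**3. Intervention rates, per 100, from the effects assumed in Protocol 8.4.**
- Half of failures and relapses are culture-positive and half of those are resistant, so 2 × 0.5 × 0.5 = 0.5 is prevented in each category.
- Susceptible relapse is cut by one third. Counting only culture-positive relapses, 0.5/3 = 0.17. Counting all relapses not resistant, 1.5/3 = 0.50.
- Default and death are each 4 × 0.8 = 3.2.
- Failure is 1.5 and relapse is 1.33 or 1.00, so the total is 9.23 or 8.90.

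The reduction of 2.77 or 3.10 points agrees with the plan's 3 points.

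**4. Effect of the clause.** OR = [a/(n₁−a)] / [c/(n₀−c)], with 95% CI exp(ln OR ± 1.96 × √(sum of reciprocal cell counts)). Loss to follow-up is treated the same way in every row. Paired values are the two relapse assumptions.

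| Leaves PP | Control | Intervention | OR (95% CI where computed) |
|---|---|---|---|
| None (no clause) | 60/500 | 46.2/500; 44.5/500 | 0.746 (0.50–1.12); 0.716 (0.48–1.08) |
| Failures | 50/490 | 38.7/492.5; 37.0/492.5 | 0.750; 0.715 |
| Failures, half of relapses | 45/485 | 35.3/489.2; 34.5/490 | 0.761; 0.741 |
| Failures, all relapses | 40/480 | 32/485.8; 32/487.5 | 0.776 (0.48–1.26); 0.773 (0.48–1.25) |
| Defaults as well | 20/460 | 16/469.8; 16/471.5 | 0.776 (0.40–1.52); 0.773 (0.40–1.51) |

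Control events removed are 10/60 = 17% if only failures leave and 20/60 = 33% if all relapses leave too. On the 10% base these are 10/50 = 20% and 20/50 = 40%. The control PP event rate falls from 60/500 = 12.0% to as low as 40/480 = 8.3%.

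**5. Category rows, per 500.** Control failures plus relapses go from 10 + 10 = 20 to as few as 0. Intervention goes from 7.5 + 6.7 = 14.2, or 7.5 + 5.0 = 12.5, to as few as 0.

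**6. Sensitivity.** Protocol 8.4 ties the reduction in death and default to unrecognised resistance, so applying it to all deaths and defaults is an assumption. At the other extreme, with no reduction in either, intervention events are 1.5 + 1.33 (or 1.00) + 4 + 4 = 10.83 (or 10.50) per 100.
- Without the clause: OR = (54.17/445.83)/(60/440) = 0.891, or (52.5/447.5)/(60/440) = 0.860.
- All failures and relapses out: OR = (40/445.83)/(40/440) = 0.987, or (40/447.5)/(40/440) = 0.983.

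The shift is larger here because nearly all the benefit lies in the categories removed. The total reduction is then only 1.17 or 1.50 points, short of the planned 3.

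**The case against.** The best defence is that the definition can be read more kindly. It admits patients who reached an endpoint earlier and who followed the protocol, the first endpoint is the one analysed, and Table 2 does not list re-treatment after an endpoint as a violation. An analyst working from Table 2 alone would keep these patients. That does not rescue the text: Table 2's silence cannot override the explicit exclusion in SAP 4.1, which fits re-treated endpoint patients better than anyone else. The text can be applied as written and is not self-contradictory. The trouble is what it produces.

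Three points on size stand. PP is a secondary analysis in a pilot estimation study, and the same failures and relapses remain visible in the primary ITT results. The composite barely moves if only failures leave. The upper figure of 20 is a maximum: the 12-month visit is the last one scheduled, the Protocol 5.1 schedule marks no treatment there and later follow-up is passive, so re-treatment of relapses found at that visit may never be recorded. The failure row is exposed more surely than the relapse row. It is also a judgement, not something the documents show, that readers would put low PP counts down to adherence.

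**Conclusion.** The concern holds. As written, PP membership depends on the outcome for failures and relapses managed according to protocol, and the protocol's own PP definition contains no such condition.

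On the plan's rates, 17% to 33% of expected control events leave PP (20% to 40% on the 10% base). With the plan's assumed effects the composite OR rises from 0.72–0.75 to at most 0.77–0.78, a modest shift that would not be visible against an interval of roughly 0.5 to 1.2. The important loss is in the failure and relapse rows, which may be largely emptied in both arms.

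These figures assume that failures are bacteriological and are re-treated, that default stays in PP except in the last table row, and that the Protocol 8.4 reductions apply as set out. If default is also out, only the 20 deaths remain of 60 control events. The primary ITT analysis, the safety analysis and the go/no-go criteria are not affected. It should be fixed, but it does not threaten the main result.

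**What to change.** In SAP 4.1 and 4.1.2, limit the single-regimen condition to regimen changes before the first study endpoint, and add a sentence such as: *PP status is judged only up to the first study endpoint; re-treatment after a declared failure or relapse does not remove a patient from PP.* Both sections need the same rule, because a second regimen and a regimen received only once are not the same test for a patient who re-starts the regimen already taken.

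Two editorial clarifications could be made at the same time: express complete follow-up as the visit 12 months after end of treatment in place of a fixed 2.5 years, and state whether default, and failure declared through a change of at least two drugs, are in PP.

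The cost is two sentences in the SAP. No new data are needed, and the ITT and safety analyses and patient management do not change.

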#### 4.2. Efficacy study endpoints

##### *Primary endpoint*

The primary efficacy endpoint is the incidence of adverse treatment outcomes. Following the WHO guidelines from 2010, as currently in use in the NTP in Bangladesh, an adverse treatment outcome is defined as any occurrence of the following:

- Relapse: Cured previously from TB or completed treatment for TB and now having bacteriologically positive sputum for TB (at 12 months follow-up or at an earlier time point)
- Default: The patient whose treatment was interrupted for 2 consecutive months or more.

- Failure: Sputum positive for TB at 5 months or later during treatment. Failure will also be declared if the regimen has to be changed for at least 2 drugs due to adverse events.
- Death: All-cause mortality between case registration and end of TB treatment (related or not to TB or TB treatment)

Patients who are transferred out will be excluded from the outcome analysis.

In line with current WHO recommendations, patients detected with MDR-TB or rifampicin resistance before any outcome applies and switched to the MDR-TB regimen will be excluded from the outcome analysis.

Analyses will be performed using the NTP smear-based recurrence (failure, relapse) definitions, but as a secondary approach culture-based definitions will be used. In each analysis, if a patient has two events for the analysis of interest, the first endpoint will be taken into account, except for cured/completed followed by relapse which is considered as relapse.

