2) Assessment of drug toxicity and initial treatment response will be performed at the time the last recruited patient finishes treatment. The data will be compiled at 9 months after the end of recruitment to ensure all treatment related data, including 8 months of treatment for retreatment cases in the control arm, are available. This analysis will be primarily performed for the go/no-go decision and design considerations for a possible next study, such as a cluster-randomized trial. The decision on proceeding to the cluster randomized study will be based on the absence of excess toxicity, a trend toward a reduction of unfavourable outcomes (excluding relapse), possible favourable effects overcoming low-resistance mutations.

3) A final analysis of the study endpoints, including relapse, will be performed one year after end of treatment of the last enrolled patients, i.e. about 2.5 years after enrolment start.

This analysis plan will be finalized and approved before database lock of the first interim analysis data. Major changes in statistical methodology used for the main and pre-planned analyses from this SAP, will require detailed description and justification in the statistical analysis report. The final analysis datasets, programs, and outputs are archived following good clinical practice guidelines (ICH E9).

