#### Treatment:

*New cases:* 2HRZE/4HR, i.e. 2 months of isoniazid, rifampicin, pyrazinamide and ethambutol intensive phase, followed by 4 months continuation phase isoniazid plus rifampicin) (Cat. 1 regimen, 6 months)

*Retreatment cases:* 2 months of SHRZE (S= streptomycin) followed by 1 month of HRZE and 5 months HRE (Cat. 2 regimen, 8 months)

Any patients with *MDR TB detected* at any time will be switched to 4KHPtoGCEZ/5GCEZ, i.e. 4 months of kanamycin, isoniazid, prothionamide, gatifloxacin high-dose, clofazimine, ethambutol and pyrazinamide, followed by 5 months of gatifloxacin high-dose, clofazimine, ethambutol and pyrazinamide (MDR regimen, 9 months)

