#### Treatment:

*New cases:* Compared to standard regimen dosing of rifampicin is doubled, while standard dose isoniazid, pyrazinamide and ethambutol are maintained, i.e. 2 months of HRhZE followed by 4 months of HRh (6 months)

*Retreatment cases:* retreatment cases randomized to the intervention arm receive the same care as new cases in the same arm.

Any patients with *MDR TB detected* at any time will be switched to 4 months of KHPtoGCEZ followed by 5 months of GCEZ (MDR regimen)

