## 8.2. Safety outcomes and analyses

### 8.2.1. *Serious adverse events*

*General aspects:* Serious adverse events (SAEs) will be coded using the Medical Dictionary for Regulatory Activities (MEDDRA) and will be reported based on MEDDRA preferred terms and body systems. All SAEs will be analyzed based on counts of patients with a specific category and not on counts of individual adverse events. The relationship between SAEs and treatment is determined by the local investigator and categorized as "drug-related" if possibly, probably or definitely related to treatment.

The following summaries will be present by treatment group:

- a. description of all deaths of patients up to 12 months after treatment stop;
- b. the total number of patients with any SAE by preferred term and body system up to 12 months after treatment stop;
- c. the total number of patients with any drug-related SAE by preferred term and body system up to 12 months after treatment stop;

Statistical tests of association, using logistic regression, adjusted for hospital and stratum (new/ retreatment case), between treatment and occurrence of SAE will be performed for the following categories:

- a. number (%) of patients with any SAE, any drug-related SAE;
- b. number (%) of patients with the most common SAEs and drug-related SAEs (most common: with an incidence of 10% or more in at least one treatment group).

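### In retreatment cases the Death component runs to month 8 on control but month 6 on intervention, which slightly favours the intervention at the go/no-go look and in the per-protocol set

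*SAP*

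**What the plan says.** **Death window.** SAP 4.2, like Protocol 3.1, counts as Death "All-cause mortality between case registration and end of TB treatment (related or not to TB or TB treatment". The window therefore lasts as long as the regimen.

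**Regimen length (SAP 2.1).**
- Control, new cases: "followed by 4 months continuation phase isoniazid plus rifampicin) (Cat. 1 regimen, 6 months".
- Control, retreatment cases: "2 months of SHRZE (S= streptomycin) followed by 1 month of HRZE and 5 months HRE (Cat. 2 regimen, 8 months".
- Intervention, new cases: "2 months of HRhZE followed by 4 months of HRh (6 months".
- Intervention, retreatment cases: "retreatment cases randomized to the intervention arm receive the same care as new cases in the same arm", so also 6 months.

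**Go/no-go analysis.** SAP section 1 places it at the end of treatment and bases the decision partly on "a trend toward a reduction of unfavourable outcomes (excluding relapse". Its data cut is timed to let the 8-month control regimen finish.

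**Final ITT analysis.** SAP 4.1.1 and 6.2b count as adverse a patient lost before the 12-month post-treatment visit, and 4.1.1 adds a patient who gives no sputum. Patients known to have left the area are excepted. That visit is timed from the end of treatment (SAP 2.1; Protocol 5.1, footnote 4).

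**Per-protocol set.** SAP 4.1.2 requires complete follow-up or a study endpoint, and Table 2 lists "Missing study endpoint" as a major violation.

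**Model.** SAP section 6 uses logistic regression on a yes/no outcome with arm, hospital and stratum. There is no term for time at risk.

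**Safety.** SAP 8.2.1 already asks for a "description of all deaths of patients up to 12 months after treatment stop".

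**The concern.** Within the retreatment stratum, the period in which a death can become an event depends on the randomised arm. A patient who dies in month 7 is an event on control and, at the go/no-go look, not an event on intervention. Adjusting for stratum does not help, because the imbalance lies between arms inside the stratum. The direction is known: it favours the intervention.

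Three results are exposed: the go/no-go comparison, the retreatment results reported separately at that time, and the per-protocol analysis. There is also a gap in classification. Neither document says how a known death after treatment is categorised for efficacy, so such a death has no clear row in the by-category table. Protocol 8.2 gives relapse followed by death as an example of two events. Because relapse follows cure or completion, that death lies outside the Death definition, and the two texts need reconciling.

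**Working it through.** The plan gives no figure for the unequal window. The benchmark is its hoped-for reduction from 10% to 7% (Protocol 8.4).

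**Check on the benchmark.** For 80% power at two-sided 5%, the uncorrected size is n = [1.960·√(2·0.085·0.915) + 0.842·√(0.10·0.90 + 0.07·0.93)]² / 0.03² = 1356 per arm after rounding up. With continuity correction, (n/4)·[1 + √(1 + 4/(0.03n))]² gives 1422 after rounding up. The stated 1421 is reproduced.

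**Inputs**
- Death risk: 4%, new and retreatment cases together (Protocol 8.4). Applying it to 6 months in retreatment cases is an assumption.
- Retreatment share: not stated for the trial. The national figure is 7366/100,000 = 7.4% (Protocol 1.1); 15% and 30% are assumed.
- Hazard shape: not stated. Constant hazard is assumed first, then varied.

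**Extra control risk in months 6 to 8**
1. Monthly hazard h = −ln(1 − 0.04)/6 = 0.0068.
2. Eight-month risk = 1 − exp(−8h) = 5.3%.
3. Difference = 5.3% − 4.0% = +1.3 points in control retreatment cases.

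**Pooled bias = share × difference**

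| 6-month death risk | Hazard in months 6–8 relative to months 0–6 | Stratum | Share 7.4% | Share 15% | Share 30% |
|---|---|---|---|---|---|
| 4% | 1 | +1.30 | +0.10 | +0.19 | +0.39 |
| 4% | 0.25 | +0.33 | +0.02 | +0.05 | +0.10 |
| 10% (assumed) | 1 | +3.11 | +0.23 | +0.47 | +0.93 |

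Entries are percentage points. For a changed hazard the stratum figure is (1 − d)·(1 − exp(−2hf)), where d is the 6-month risk and f the relative hazard.

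If the 4% is instead read as an 8-month risk, the 6-month risk is 3.0% and the stratum difference is 1.0 point.

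In the first row the pooled bias is 0.5 to 1.9 deaths per 500 patients, or 3% to 13% of the hoped-for 3 points. From a 10% base it gives a spurious pooled odds ratio of 0.99 to 0.96. The two-sided rejection rate with no true effect is 0.050 to 0.055. At the extreme of the assumed range (10% death risk, 30% share) the odds ratio is 0.905 and the rejection rate 0.077.

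**Where it applies**
- *Go/no-go:* 8 versus 6 months. The 12-month visit plays no part.
- *Final ITT:* if the no-sputum rule catches post-treatment deaths, follow-up is 8 + 12 = 20 months versus 6 + 12 = 18. With the same h, 12.7% − 11.5% = +1.2 points (unrounded 1.20), so the 2-month gap remains.
- *Per-protocol:* a post-treatment death is neither a defined endpoint nor complete follow-up. On a plain reading, a month-7 death counts on control and removes the patient on intervention.

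**The case against.** The strongest reply is that a reader might infer that deaths after treatment are ignored throughout. The documents do not support that. ITT is the primary approach, and its rule for patients without a 12-month sputum, read literally, already makes most later deaths adverse. This stands, and it limits the point to the go/no-go look, the retreatment subgroup at that time, the per-protocol set and a residual 18-versus-20-month gap.

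Other replies have force:

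- **Size.** At a 7.4% share there are about 37 retreatment patients per arm (0.074 × 500), and the artefact is about half a death. The interaction test in SAP 6.1 is also conditional on enough events.
- **Default.** A reader might add default, which has the same unequal exposure, and obtain a larger figure. Default on a longer regimen can fairly be seen as a real consequence of the strategy being compared, so it is left out here.
- **Definition.** On-treatment death is a stated adoption of programme outcomes, and a fixed window is partly a choice of estimand. That supports keeping the programme definition as a secondary table. It does not justify an arm-dependent window in the main comparison.
- **Decision.** The go/no-go choice looks for a trend alongside toxicity and mutation data, in a pilot that disclaims formal testing. The bias therefore does not by itself settle the decision.
- **Per-protocol.** The Table 2 entry is not defined further, so its application to post-treatment deaths is inference, although it is the plain reading.
- **Category.** Protocol 8.3.1 and 8.3.6 count patients lost to follow-up as failures, which could supply a category. The SAP says only that they are adverse outcomes, and neither text addresses a known death.

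**Conclusion.** The point holds as a minor one, confined to the retreatment stratum. The death window differs by arm (8 versus 6 months), the direction favours the intervention, and the planned model cannot remove it. On the Protocol's 4% death rate, taken as a 6-month risk with constant hazard, it adds 1.3 points in control retreatment cases and 0.10 to 0.39 points pooled for shares of 7.4% to 30%. If the hazard falls to a quarter after month 6, the pooled figure is 0.02 to 0.10. The trial's retreatment share, the death rate in retreatment cases and the hazard shape are not in the documents, so these are ranges under stated assumptions.

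A reader might conclude that the primary result is materially biased. The documents do not support this. The final ITT rule captures most later deaths, and the pooled effect is small against 3 points. The correction is still worthwhile, because it removes a bias of known direction at almost no cost and closes a real gap in how post-treatment deaths are classified.

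**What to change.** In SAP 4.2, count all-cause death from randomisation to the same month in both arms, using the shorter window:

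- **Go/no-go analysis:** in retreatment cases, count deaths to month 6 in both arms. Month 8 would not work without new data. Patients on 6-month regimens have no visit between V8 and V9, and Protocol 7.1 registers serious adverse events only to the end of treatment.
- **Final analysis:** count deaths to month 18 from randomisation in both arms, using dates of death obtained by V9. Setting the cut-off at the 12-month visit itself would restore the 2-month gap.
- **Classification:** class known post-treatment deaths within the window as death in ITT, per-protocol and the by-category table. State in SAP 4.1.1 that the no-sputum rule does not apply to a known death after month 18, since it would otherwise bring back the later control deaths.
- **Secondary table:** keep the programme definition.

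The cost is SAP wording. SAP 8.2.1 already needs deaths to 12 months after treatment. The V9 enquiry of relatives in Protocol 5.3 mentions death from TB, so staff should record any death and its date. The downsides are a small departure from programme outcome categories and the loss of control retreatment deaths in months 6 to 8 from the go/no-go comparison.
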